9.3.3 Safety

Safety Endpoints:

- Adverse events
- Local tolerability including:
 - erythema
 - edema
 - scabbing/crusting
 - vesiculation
 - erosion
 - stinging
 - burning
 - pruritis
- Clinical laboratory assessments.

9.3.4 Baseline Assessment

Descriptive statistics will be performed on relevant Visit 1 and Visit 2 data (*i.e.*, data collected prior to the treatment administration) and on demographic and baseline disease severity characteristics. There will be no statistical hypothesis testing of baseline data.

9.3.5 Efficacy Analyses

9.3.5.1 Overview

Analyses of efficacy parameters collected at the tumor level will primarily be performed at the tumor level, under the assumption that tumor responses within the same subject will be predominantly statistically independent. Those parameters include results based on tumor dimensions, SSA and PTA evaluations, and responder analyses based on any of these measures. This approach is consistent with the topical application of the study medication to individual tumors and the assumption of minimal systemic absorption or systemic action of the study medication. The statistical assumption of within-subject tumor response independence will be evaluated using the appropriate Shrout-Fleiss intraclass correlation based on tumor changes from

baseline. For this study, that statistic is assumed to be less than 0.25. If this assumption is confirmed, analyses conducted at the subject level will then be performed as supplementary analyses. Tumor volume is the primary measurement of interest; however, the ruler measurements of tumor area, length, width and height will also be analyzed as supplementary analyses, using the analysis models applied to tumor volume.

If the Shrout-Fleiss intraclass correlation statistic is equal to or greater than 0.25, then subject-level efficacy parameter analyses will be considered primary, and tumor-level efficacy parameter analyses will be considered supplementary. In either case, results from both types of analyses will be presented.

9.3.5.2 Contrasts

In order to fully understand the dose response results and achieve greater sensitivity to detect effectiveness for the active treatments, comparisons among the three treatment groups will include the following: pairwise contrasts between each active treatment group vs vehicle; a contrast between the [REDACTED] treatment group and the [REDACTED] treatment group; and a contrast between the average of the [REDACTED] and [REDACTED] treatment groups vs vehicle. In addition, all analyses and contrasts will be conducted separately for each lesion body location: Face, anterior trunk, and upper extremities.

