	
Analyses of efficacy parameters collected at the tumor level will primarily be performed at the tumor level, under the assumption that tumor responses within the same subject will be predominantly statistically independent. Those parameters include results based on tumor dimensions, SSA and PTA evaluations, and responder analyses based on any of these measures. This approach is consistent with the topical application of the study medication to individual tumors and the assumption of minimal systemic absorption or systemic action of the study medication. The statistical assumption of within-subject tumor response independence will be evaluated using the appropriate Shrout-Fleiss intraclass correlation based on tumor changes from baseline. For this study, that statistic is assumed to be less than [REDACTED]. Analyses conducted at the subject level will then be performed as supplementary analyses. Tumor dimension analyses will include tumor volume derived from measurements by ruler, which will be the primary assessment. Tumor volume is the primary measurement of interest; however, the ruler measurements of tumor length, width, height and area will also be analyzed as supplementary analyses, using the analysis models applied to tumor volume.
 
If the Shrout-Fleiss intraclass correlation statistic is equal to or greater than [REDACTED] then subject-level efficacy parameter analyses will be considered primary, and tumor-level efficacy parameter analyses will be considered supplementary. In either case, results from both types of analyses will be presented.
 
Contrasts:
 
In order to fully understand the dose response results and achieve greater sensitivity to detect effectiveness for the active treatments, comparisons among the three treatment groups will include the following: pairwise contrasts between each active treatment group vs vehicle; a contrast between the [REDACTED] treatment group and the [REDACTED] treatment group; and a contrast between the average of the [REDACTED] and [REDACTED] treatment groups vs vehicle. In addition, all analyses and contrasts will be conducted separately for each lesion body location: Face, anterior trunk, and upper extremities.
 
Endpoints:
 
The safety endpoint is to determine the safety of treatment with NFX-179 Gel [REDACTED] and [REDACTED] or Vehicle Gel applied QD for 182 days of treatment. The results of safety and local tolerability assessments including pain/burning, itching, erythema, edema, scabbing/crusting, and vesiculation/erosion will be summarized by treatment group and visit. The evaluation of adverse events will be based on summaries and listings of adverse events by treatment group, as described below under Safety Analyses.
 
If tumor independence is confirmed as discussed above, the primary efficacy endpoint will be a dichotomized analysis conducted on the proportion of tumors achieving a reduction from baseline volume of at least 50%. A Chi-square analysis at the tumor level will be performed as the primary analysis between vehicle and each active treatment group. Otherwise if tumor

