Number the Target cNFs at Visit 1 starting with 1 and proceeding up to 10 with no number omitted or reused. Target cNFs 1 and 2 must be on the face and Target cNFs 3-10 must be on the anterior trunk or upper extremities. If only 1 Target cNF is identified on the face, Target cNF 1 must be on the face and Target cNFs 2-10 must be on the anterior trunk or upper extremities.

For identification in the study photographs with the Target cNF centered in the large template cutout place 2 appropriately numbered Identification (ID) stickers in the small template cutouts (diagram not to scale):

Write the Target cNF Number on at least one ID sticker. Both ID stickers must be visible in the photographs.

The investigator will document the location of each Target cNF on the Visit 1 body charts using the following process:

- Make a circle or similar mark identifying the location of each Target cNF
- Write the Target cNF Number adjacent to the mark
- Also report at least the following additional information on the body charts:
 - Protocol number
 - Subject Identifier.

At Visit 1 and Visit 2, the investigator or designee will dispense a photocopy of the body charts to the subject. New, eligible Target cNF(s) may be selected at Visit 2 if necessary. The investigator or designee will place the original Visit 1 and Visit 2 body charts in the subject's study file.

The investigator or designee must report the approximate location of each Target cNF identified at Visit 1 in the CRFs and include the Target cNF Number.

At Visit 2, the investigator will use the Visit 1 body charts and photographs to identify the location of the 10 Target cNFs identified at Visit 1. If the 10 Target cNFs identified at Visit 1 don't meet eligibility criteria, new eligible Target cNF(s) may be selected at Visit 2.

At Visits 3-9, prior to any Target cNF assessments, an investigational center staff member other than the evaluating investigator will use the Visit 2 body charts and study photographs to identify the location each Target cNF for the study evaluations. A staff member will use the cNF template, center each Target cNF in the large circular cutout and place the 2 ID stickers, numbered as appropriate on the subject's skin.

The investigator is not allowed to participate in the photography process or to use the study photographs to assist with any Target cNF evaluations EXCEPT as noted below:

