for whom at least 5 treated tumors showing the greatest tumor-level percent reduction from baseline volume have a percent reduction from baseline of at least 50%. A Chi-square analysis with contrasts as outlined above will be used. At the subject-level analysis, an Analysis of Variance will also be used to analyze the per-subject mean percent of tumor responders, with contrasts as described above. Treatment groups may also be compared using appropriate mixed-model logistic regression incorporating both tumor- and subject-level information. Supplementary analysis similar to those described above will also be conducted based on threshold reductions from baseline volume of at least 25%, 30%, 60% and 75%. The first secondary efficacy endpoint is to determine the clinical efficacy of NFX-179 Gel defined as the mean percent change in neurofibroma volume after 182 days of treatment based on tumor volume derived from ruler measurements. Analyses of Variance will be conducted both on the tumor level and the subject level, including the contrasts as described above. The determination of whether the tumor-level or subject-level analysis will be considered preferentially will be based on the outcome of the tumor independence assessment described above. The non-primary analysis will be considered as a supplementary analysis. Additional secondary efficacy endpoints include the analysis of change from baseline in the Physician's Tumor Assessment grade and the Subject's Self-Assessment grade after 182 days of treatment. These will be analyzed analogously to the primary endpoint using an Analysis of Variance and contrasts described above. In addition, for each assessment dichotomized analyses will be conducted on the proportion of tumors achieving a grade of Clear, the proportion of tumors achieving a grade of either Clear or Almost Clear, the proportion of tumors achieving at least a grade 1 improvement, and also a 2 grade or greater improvement from baseline after 182 days of treatment. Treatment groups will be compared using separate Chi-square analyses. An appropriate mixed-model logistic regression may also be used, as well as an ANOVA analysis of within-subject averaged results across tumors. Contrasts as described above will be used.

Analyses similar to those described above will be conducted based on tumor area and tumor length.

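### The subject-level Responder rule needs 5 responding tumors, yet it is repeated by body location, and the face has only 1 or 2 Target cNFs, so nobody can be a facial Responder

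*Combined protocol and SAP*

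**What the plan says.** Three provisions of the combined protocol and SAP meet here.

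- **The rule.** Under Section 9.3.5.3, a subject-level Responder is a subject "for whom at least 5 treated tumors showing the greatest tumor-level percent reduction from baseline volume" reach a reduction of at least 50%. The test is a chi-square with the contrasts of Section 9.3.5.2. Similar supplementary analyses are planned at thresholds of 25%, 30%, 60% and 75%.
- **The repeat by location.** Section 9.3.5.2 states that "all analyses and contrasts will be conducted separately for each lesion body location: Face, anterior trunk, and upper extremities". The synopsis, under Contrasts, says the same.
- **The tumor count.** In the preferred case, Section 6.3 requires that "Target cNFs 1 and 2 must be on the face and Target cNFs 3-10 must be on the anterior trunk or upper extremities". The alternative reads "If only 1 Target cNF is identified on the face, Target cNF 1 must be on the face", with numbers 2 to 10 off the face. The synopsis and Sections 4.1, 5.2.1 and 6.2.1 agree.

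Section 9.3.5.1 makes the subject-level analysis primary if the intraclass correlation is 0.25 or more and supplementary otherwise. It adds: "In either case, results from both types of analyses will be presented". The subject-level Responder analysis is therefore produced whatever the correlation turns out to be.

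Section 9.3.5.3 also plans a second subject-level analysis of the same responses: "an Analysis of Variance will also be used to analyze the per-subject mean percent of tumor responders, with contrasts as described above".

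**The concern.** A fixed count of 5 is workable for 10 tumors per subject. It does not carry over to a location that holds 1 or 2. No location-specific count is given, the Responder analysis is not exempted from the repeat, and the plan does not say outright whether a subject with fewer than 5 Target cNFs at a location is a Non-Responder there or is not evaluable.

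The face result therefore carries no information about the drug. On the trunk and upper extremities, the result depends partly on where each subject's tumors were chosen. If the gap is left open, a replacement rule may be picked after results are known, and the choice of rule changes the rates considerably.

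**Working it through.** **The plan's own figure.** The only sample-size figure is power of at least 90% at two-sided alpha 0.05, with about 168 subjects randomized and at least 150 completing (Section 9.1). It cannot be reproduced because both responder rates are redacted. The point does not rest on it.

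**Inputs.** Responders need 5 tumors (9.3.5.3). Each subject has 10 Target cNFs, of which 2 are on the face and 8 elsewhere, or 1 on the face and 9 elsewhere (6.3). There are 4 contrasts (9.3.5.2): two of active against vehicle, one of active against active, and one of the average of the actives against vehicle. There are 5 thresholds, the main 50% and four supplementary (9.3.5.3).

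**Face.** With k tumors at a location and per-tumor response probability p, P(Responder) = P(X ≥ 5), where X cannot exceed k. For k = 1 or 2 this is 0 for every p, including p = 1.

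- If subjects with fewer than 5 tumors count as Non-Responders, every arm has 0 Responders (0/50 against 0/50 at the planned completers). The expected counts in the Responder cells are 0 and the chi-square is undefined.
- If they are not evaluable, no subjects remain.

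Either way, 4 contrasts at Visit 8 are empty at the 50% threshold. If the other thresholds keep the count of 5, which the plan does not state explicitly, the number is 4 × 5 = 20 per analysis population.

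**Trunk and upper extremities.** Let t tumors lie on the trunk and n − t on the upper extremities. Reaching 5 on both needs 10, more than the 8 or 9 available.

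| Non-facial tumors n | Possible splits | Only trunk can reach 5 | Only upper extremities can | Neither | Both |
|---|---|---|---|---|---|
| 8 | 9 | 4 | 4 | 1 (4/4) | 0 |
| 9 | 10 | 5 | 5 | 0 | 0 |

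These are counts of possible splits, not probabilities. The plan does not give the distribution of splits. The share of subjects unable to qualify on either site could therefore be anywhere from 0% to 100% with 8 non-facial tumors. With 9 it is 0%, provided all remain treated and measured.

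Even where 5 can be reached, the bar moves with the split. Binomial P(X ≥ 5), with independent tumors and assumed p:

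| Tumors counted | p = 0.3 | p = 0.5 | p = 0.7 |
|---|---|---|---|
| 5 at one site | 0.002 | 0.031 | 0.168 |
| 8 at one site | 0.058 | 0.363 | 0.806 |
| All 10 | 0.150 | 0.623 | 0.953 |

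**A proportional rule, for comparison.** This is P(at least half of the tumors respond) for 1, 2 and 10 tumors. The ICC column uses a beta-binomial with an assumed correlation of 0.25 between binary responses. That is not the same quantity as the plan's correlation of changes from baseline.

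| Assumed p | Independent: 1 / 2 / 10 | ICC 0.25: 1 / 2 / 10 |
|---|---|---|
| 0.1 | 0.100 / 0.190 / 0.002 | 0.100 / 0.167 / 0.060 |
| 0.3 | 0.300 / 0.510 / 0.150 | 0.300 / 0.458 / 0.273 |
| 0.5 | 0.500 / 0.750 / 0.623 | 0.500 / 0.688 / 0.556 |

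**The case against.** The strongest reply is that little is lost. The repeat by location is additional to the main comparison, no power claim rests on it, and facial efficacy can still be estimated from the tumor-level proportion, the per-subject percent of responders and the percent change in volume. An empty facial table is visibly empty and misleads nobody. All of this stands, and it limits the weight of the point.

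It is also fair that tumor locations are settled before randomization, so the split between trunk and upper extremities is a baseline feature, balanced between arms in expectation. Neither handling of subjects with fewer than 5 tumors by itself biases the arm comparison. The cost is lost sensitivity and a by-site rate that is hard to interpret.

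Read strictly, the definition makes a subject without 5 such tumors a Non-Responder. That settles the classification, but it gives 0% on the face in every arm.

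Section 5.6.9 lets a subject continue with fewer than 10 treated tumors. A 5/4 split could then become 4/4 if a stopped tumor no longer counts as treated, so the 0% for 9 non-facial tumors is a best case.

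Two possible rescues fail. The face cannot hold 5 Target cNFs, because the one-face case puts 9 elsewhere and the numbering keeps 3 to 10 off the face. Classifying subjects on all 10 tumors and then reporting by location does not help either: every subject has a facial tumor, so the face result would repeat the overall one. Nor does the plan label the repeat by location exploratory, as Section 9.3.5.3 does for earlier visits.

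**Conclusion.** The rule is wrong as written for the analyses by location. On the face it allows 0 Responders in every arm whatever the drug does, which empties 4 contrasts at the 50% threshold (20 if the other thresholds keep the count of 5). On the trunk and upper extremities, each subject can qualify on at most one site, and which site is fixed by tumor placement. The face result follows from counting alone and needs no redacted figure. Only the illustrative probabilities rest on assumed response rates and correlation.

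The scope is limited. The all-location primary analysis, at tumor or subject level, is untouched, as are the tumor-level proportions, the per-subject ANOVA and the percent-change analyses by location. The correction should still be made before unblinding, because the plan commits to an analysis that cannot be computed on the face.

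**What to change.** In Sections 9.3.5.2 and 9.3.5.3 and in the synopsis, state that the 5-tumor Responder rule, at every threshold, applies only to the all-location analysis. State that the subject-level responder result by location is the percent of a subject's Target cNFs at that location meeting the threshold, among subjects with at least one Target cNF there, analyzed with the ANOVA already planned.

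If a dichotomized result by location is also wanted, pre-specify a proportional rule, for example at least half of that location's Target cNFs (mirroring 5 of 10), and label it as a different definition from the all-location Responder.

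The cost is one or two sentences in each place, with no change to data collection or sample size. Without the proportional rule, no dichotomized subject-level rate is reported by location, and the facial percent can take only the values 0, 50 or 100 (0 or 100 with one facial tumor). With it, the bar differs by tumor count: at an assumed 30% per-tumor response and independent tumors, it is met by 30% of subjects with 1 tumor, 51% with 2 and 15% with 10.

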5.1 Number of subjects

Approximately 168 subjects will be randomized to 1 of the 3 study medication treatment groups at approximately 27 United States (US) investigational centers with the goal of at least 150 randomized subjects completing the study.

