9 STATISTICAL METHODOLOGY

9.1 Sample Size Determination

This is a Phase 2b study designed to evaluate the safety and efficacy of two doses of NFX-179 Gel in comparison to Vehicle Gel. Approximately 168 subjects with cNF are planned to be randomized in the study. The sample size has been chosen to assure at least 150 randomized subjects complete the study. It is based on the assumption that the proportion of responders will be approximately [REDACTED] in the vehicle treated group and at least [REDACTED] in the most effective active treated group. Alpha two-tail is 0.05. Under these assumptions power is expected to be at least 90% given the planned sample size.

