9.3.2 Analysis Populations and Missing-Data Imputation

All subjects who are randomized and dispensed study drug and have at least one post-baseline visit with efficacy evaluations will be included in the intent-to-treat (ITT) population.

Missing data imputation procedures based on the ITT population are described below. The Observed Cases (OC) population will include all subjects in the ITT population with observed efficacy data at Visit 8. No data imputation will be used with this population for subjects with missing data at any post-baseline visit.

The Observed Cases (OC) population will be used for primary and secondary efficacy analyses to address the main efficacy evaluation objective of the study. There will also be two sensitivity analyses of efficacy. For the first sensitivity analyses, the Per-Protocol (PP) population, drawn from the OC population subjects who completed the study through Visit 8 with no major protocol violations, will be used. For the second sensitivity analyses, the ITT population will be used, and all missing post-baseline efficacy data will be imputed using last observation carried forward (LOCF) from the last available observed efficacy data after the Baseline visit. Mixed Model-based missing data imputation or Multiple Imputation may be used as a supplementary imputation method. A supplemental efficacy analysis based specifically on subject Responders will also be conducted using the ITT population where subjects terminating the study before completing Visit 8 due to treatment-related adverse events will be imputed as Non-Responders. All efficacy analyses will perform separate

comparisons of each Active treatment group with the Vehicle group along with other contrasts described below. No adjustments for multiplicity will be made. All subjects who are randomized, received at least one confirmed dose of study drug, and have at least one post-baseline safety evaluation will be included in the Safety Population.

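### Efficacy is also analyzed separately for face, trunk and upper extremities with no treatment-by-location test, so a uniform effect can look location-specific, and the fallback Responder rule cannot be met on the face

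*Combined protocol and SAP*

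**What the plan says.** Section 9.3.5.2 (repeated in the synopsis) defines four contrasts: the "pairwise contrasts between each active treatment group vs vehicle" (two of them), one dose against the other, and the average of the active arms against vehicle. It then states that, as an addition to these, "all analyses and contrasts will be conducted separately for each lesion body location: Face, anterior trunk, and upper extremities". Section 9.3.2 states "No adjustments for multiplicity will be made".

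Numbers per location are unequal by design. In Section 6.3, "Target cNFs 1 and 2 must be on the face and Target cNFs 3-10 must be on the anterior trunk or upper extremities"; the permitted alternative is one facial tumor and nine elsewhere. The split between trunk and upper extremities is not specified.

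Section 9.3.5.1 makes the tumor-level analysis primary if the Shrout-Fleiss intraclass correlation (ICC) is below 0.25, and the subject-level analysis primary otherwise. In Section 9.3.5.3 the subject-level primary analysis counts a subject as a Responder when at least five treated tumors have shrunk by at least 50%.

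No section plans a treatment-by-location interaction or heterogeneity test. The mixed-model logistic regression in Section 9.3.5.3 is optional and names no location term. Section 9.5 does not list location among its subgroups. Analyses at earlier visits (Section 9.3.5.3) and subgroup analyses (Section 9.5) are called exploratory; the location analyses are not.

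**The concern.** Three sets of p-values, one per location, invite the reader to set a significant result beside a non-significant one and conclude that the drug works in one place and not in the other. That comparison is not a test of difference. The face carries 10% to 20% of the tumors, so under a uniform effect it is the location most likely to miss significance unless trunk or upper extremities happen to hold equally few. Location also varies within each subject, and separate analyses make no use of that within-subject comparison.

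The fallback primary analysis adds a structural problem. If all analyses are repeated by location, so is the Responder rule, which needs more tumors than the face has. A table showing no facial responders in any arm would be a product of the definition. At stake is the reading of the supportive location results, not the pooled primary test.

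**Working it through.** **Plan's own figure.** Section 9.1 states "Alpha two-tail is 0.05" and "Under these assumptions power is expected to be at least 90% given the planned sample size". This cannot be reproduced: the assumption reads "the proportion of responders will be approximately [REDACTED] in the vehicle treated group and at least [REDACTED] in the most effective active treated group", and the unit of sizing (subject or tumor) is not given. The redaction is not a fault of the plan, but it forces a range. No power is stated by location.

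**Inputs from the documents.** 1:1:1 allocation, "with the goal of at least 150 randomized subjects completing the study" (Section 5.1), so 150/3 = 50 per arm; ten tumors each, so 500 tumors per arm; face 50 × 1 = 50 to 50 × 2 = 100 tumors per arm.

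**Assumed inputs.** Vehicle rate 5% to 30%; trunk/arm split varied (for example 200/200, 225/225, 350/100 tumors per arm); every subject has tumors in all three locations, which is optimistic for trunk and arms.

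**Step 1: rates consistent with 90% power.** Power = Φ[(d − 1.96·s₀)/s₁], with d the difference in rates, s₀ = √(2·p̄(1−p̄)/n) and s₁ = √((p₀(1−p₀)+p₁(1−p₁))/n). Solve for the active rate p₁ giving 90% under three readings of n per arm: (A) 50 subjects; (B) 500/(1 + 9 × 0.25) = 154 effective tumors; (C) 500 independent tumors.

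**Step 2: same true rates in every location.** Compute power P₁, P₂, P₃ by location, then P(mixed) = 1 − P₁P₂P₃ − (1−P₁)(1−P₂)(1−P₃).

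Example, reading B, 10% vs 23.7%, tumors 100/200/200: face power 0.741, the others 0.959 each. P(mixed) = 1 − 0.741 × 0.959² − 0.259 × 0.041² = 0.32.

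Example, reading C, 10% vs 17.0%, same tumors: powers 0.303, 0.534, 0.534. P(mixed) = 1 − 0.303 × 0.534² − 0.697 × 0.466² = 0.76.

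| Reading | Rates (vehicle 10%) | Face power | Power elsewhere | Mixed pattern, best dose vs vehicle |
|---|---|---|---|---|
| A: 50 subjects, same rates per tumor | 10% vs 36.9% | 90–99.6% | at least 99.6% | 0.3–10% |
| B: 154 effective tumors | 10% vs 23.7% | 45–74% | 74–99.8% | about 30–67% |
| C: 500 tumors | 10% vs 17.0% | 17–30% | 30–77% | 76–83% |

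Other vehicle rates from 5% to 30% change these figures very little. The formula treats locations as independent. Beta-binomial simulation with ICC 0.24 lowers reading C to 53–62% and leaves A low (about 1–9%).

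**Step 3: other planned tests.** Under reading A, if the other dose has half the effect (assumed), that dose vs vehicle is mixed in 27–67% of trials and dose vs dose in 51–77%. For the subject-level ANOVA of percent of tumors responding, sized for 90% power overall at ICC 0.25–0.40, the pattern is mixed in 27–56%.

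**Step 4: the five-tumor rule.** The face has at most 2 tumors, and 2 < 5, so no subject can qualify there. Trunk and upper extremities share 8 or 9 tumors, and 5 + 5 = 10 > 9, so at most one location per subject can ever qualify. No assumed rate is needed.

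**Step 5: with a heterogeneity test.** In the same simulations, a 2-df test of treatment by location declares a uniform effect location-specific in 5.0–5.5% of trials with independent tumors, and in 2–4% at ICC 0.10–0.24 when it ignores clustering (conservative).

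**The case against.** The strongest reply is that these analyses are supplementary. Section 9.3.5.2 introduces them as additional, neither the primary test in Section 9.3.5.3 nor the objectives in Section 3 mention location, and no success criterion, dose choice or stopping rule uses a location result. That stands, and it limits the point to interpretation.

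A reader might infer that a uniform effect will often look location-specific. The documents do not support that as a general statement. If the redacted rates were sized on 50 subjects per arm and also apply per tumor, best dose vs vehicle gives a mixed pattern in at most about 10% of trials. A figure of 19–53% arises for 10% vs 25–30% or 15% vs 30–35% with subject-level tests, ICC 0.1–0.4, 70% of subjects having two facial tumors and a 60/40 trunk/arm split. That is one assumed scenario: at 50 subjects per arm those rates have only 43–71% power, so on subject-level sizing they are smaller effects than the plan assumes.

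A reader might also infer that development will be steered away from the face. Nothing in the documents says so. Error across the many unadjusted location tests is a separate matter, disclosed in Section 9.3.2, and an interaction test does not cure it.

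Separate reporting is reasonable in itself: facial tumors may be 5 mm long, whereas others must be at least 7 mm (Section 5.2.1). That supports descriptive tables by location. It also means an interaction test cannot by itself separate location from tumor size.

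**Conclusion.** The point holds as a matter of interpretation. The plan repeats all efficacy analyses by location without a test of whether the effect differs, without an exploratory label, and with only 10–20% of tumors on the face. Under a uniform effect, a mixed pattern for best dose vs vehicle occurs in under 1% to about 80% of trials; where in that range this trial lies depends on the redacted rates, the unit of sizing and the assumed trunk/arm split. Even in the favorable case, a weaker dose or the dose comparison can give mixed patterns much more often.

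The Responder-rule consequence needs none of these assumptions: if the ICC is 0.25 or more and the rule is applied by location as written, facial response is 0% in every arm. The pooled primary result stands in either case. The change should be made, but the trial does not depend on it.

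**What to change.** In Section 9.3.5.2 and the synopsis:

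- Add one pre-specified model per endpoint with treatment, location and treatment-by-location terms, and subject as random effect or cluster.
- Take location-specific treatment estimates and 95% CIs from that model.
- Claim a difference between locations only on the interaction test. State its form: 2 df for each active arm vs vehicle, or (3 − 1) × (3 − 1) = 4 df overall.
- Label all location results exploratory.
- Within a location, use tumor-level response or the per-subject percent of tumors responding, and state that the five-tumor rule applies only to all ten tumors together.
- Keep the descriptive tables by location.

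The cost is SAP wording and one additional model per endpoint; no data collection or sample size changes. The drawback is that the interaction test has limited power, so some real differences between locations will stay unproven. The confidence intervals will show that uncertainty.
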